## 7.3 Subject Population(s) for Analysis

- Protocol-compliant population: Any subject who was randomized and received the protocol required study drug exposure and required protocol processing will be the primary analysis population.
- All-treated population: Any subject randomized into the study that received at least one dose of study drug will be subject to secondary analyses.

# 8 Safety and Adverse Events

#### 8.1 Definitions

#### Adverse Event

An *adverse event* (AE) is any symptom, sign, illness or experience that develops or worsens in severity during the course of the study. Intercurrent illnesses or injuries should be regarded as adverse events. Abnormal results of diagnostic procedures are considered to be adverse events if the abnormality:

- results in study withdrawal
- is associated with a serious adverse event
- is associated with clinical signs or symptoms
- leads to additional treatment or to further diagnostic tests
- is considered by the investigator to be of clinical significance

AE Classification. The following definitions were based on guidelines provided by the Office for Human Research Protections (OHRP). The following URL provides useful examples to help clarify classification of adverse events https://www.hhs.gov/ohrp/regulations-and-policy/guidance/reviewing-unanticipated-problems/index.html

An AE is deemed an *unanticipated problem* if it is not expected given (a) the known or foreseeable risk of the study procedures that are described in the informed consent document or study protocol, (b) the characteristics of the population being studied, (c) related or possibly related to participation in the study, and (d) suggests the research places subjects are greater risk of harm than previously known.

#### Serious Adverse Event (SAE)

Adverse events are classified as serious or non-serious. A *serious adverse event* is any AE that is:

- fatal
- life-threatening
- requires or prolongs hospital stay
- results in persistent or significant disability or incapacity
- a congenital anomaly or birth defect
- an important medical event

Important medical events are those that may not be immediately life threatening, but are clearly of major clinical significance. They may jeopardize the subject, and may require intervention to prevent one of the other serious outcomes noted above. For example, drug overdose or abuse, a seizure that did not result in in-patient hospitalization, or intensive treatment of bronchospasm in an emergency department would typically be considered serious.

All adverse events that do not meet any of the criteria for serious should be regarded as **non-serious adverse events**.

### Adverse Event Reporting Period

The study period during which adverse events must be reported is normally defined as the period from the initiation of any study procedures to the end of the study treatment follow-up. For this study, subjects will be followed for AEs from the time of voxelotor administration until 2 days after the last administration of voxelotor as defined by the wash out period.

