# 3 Study Design

## 3.1 General Design

Following a screening period and observation that clinical status is stable and requiring substantial oxygen support for 48 hours, subjects with decompensation of ESLD or ALI with hypoxemia, will be approached for informed consent. The nature of the risks and benefits associated with participation in the study will be explained to all potential study subjects or legally authorized representative (LAR). Written informed consent must be obtained before the subject can begin any screening procedures that are not considered standard patient care.

**Physiological data:** Physiological data at screening, baseline, study day 1-5, and up to two days post voxelotor administration will be recorded from standard of care with the only exception being SpO2/FiO2 (S/F) ratio measurements, which will be obtained at the same intervals but by the qualified and delegated study staff or medical team through the use of an FiO2 weaning maneuver.

Physiological measures to be recorded are detailed on the Schedule of Activities table 2.

**FiO2** Weaning Maneuver: The process of titrating FiO2 down slowly until the study patient's SpO2 measurement is approximately 88%. This will provide the study team with values for an S/F ratio that more closely represents the transition to the steepest part of the oxygen dissociation curve (ODC). Measurements that represent this transition on the ODC will allow for more precise comparison and provide more accurate trending data. Once completed, the oxygen delivery system will be titrated back to achieve SpO2 goals prescribed by the medical team.

**Modified Borg Dyspnea Scale:** Study subjects will be asked to rate their dyspnea symptoms daily to record their perceived shortness of breath.

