#### 7.2 Statistical Methods

Descriptive statistics for patient characteristics and baseline factors will be presented as median and interquartile range for continuous variables and number and percentage for categorical variables. The primary outcome will be change in S/F ratio from baseline to 2 days after initiation of voxelotor treatment, and the secondary outcome will be change in S/F ratio from baseline to 5 days after initiation of voxelotor treatment. Each will be compared using the Wilcoxon Signed Rank test. The baseline value will be defined as the median S/F ratio measurement during the 48-hour period before initiation of voxelotor treatment. Similarly, the

\*only if feasible/ ambulatory patients only. Exercise protocol is SOC and data collected will be reviewed from medical record.

day 2 and day 5 S/F ratio values will be defined as the median S/F ratio measurement on the second and fifth days after initiation of treatment.

All S/F ratio values will also be analyzed using a mixed-effects model with a random intercept for each patient and time in hours (relative to initiation of voxelotor treatment) as a fixed effect. Quadratic and cubic terms for time will also be included to allow for flexible modeling of treatment effect over time. We will tabulate and report all observed adverse events occurring during this trial.

For the ALI group with an arterial line in place, the PaO2/FiO2 (P/F) ratio will also be compared in a similar manner to identify whether any improvement in S/F ratio is due to clinical improvement of ALI, as reflected in the P/F ratio. The concept of Voxelotor use is an improvement in the S/F ratio (the result of left-shift in p50) for a given P/F ratio (the result of pulmonary function limiting PaO2). This may be especially important for the ALI sub-study cohort, as ALI could improve during the 5 day dosing period. Realistically, however, such progress is typically slow and, in contrast, the end-stage lung disease cohort would not be expected to improve and S/F ratio alone would reflect voxelotor effect without the need to track P/F ratios.

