## 8.2 Recording of Adverse Events

At each contact with the subject, the investigator must seek information on adverse events by specific questioning and, as appropriate, by examination. Information on all adverse events should be recorded immediately in the source document of the case report form (CRF). All clearly related signs, symptoms, and abnormal diagnostic procedures results should be recorded in the source document, though should be grouped under one diagnosis.

All adverse events occurring during the study period must be recorded. The clinical course of each event should be followed until resolution, stabilization, or until it has been determined that the study treatment or participation is not the cause. Serious adverse events that are still ongoing at the end of the study period must be followed up to determine the final outcome. Any serious adverse event that occurs after the study period and is considered to be possibly related to the study treatment or study participation should be recorded and reported immediately.

Requirements for reporting of an AE to various entities (IRB, FDA, and Sponsor) differ according to whether or not the AE represents an unanticipated problem. This study will follow 21 CFR 312.32 IND Safety Reporting guidelines and DUHS prompt reporting to the IRB policy for events that occur with this study.

Subjects in this study will be followed for AEs from the time of voxelotor administration until 2 days after the administration of voxelotor as defined by study wash out period. The PI will be responsible for ensuring participants' safety.

[name] will be the physician responsible for reviewing and evaluating all adverse events. [name] will evaluate the safety of voxelotor treatment in all subjects by following adverse events and assigning likelihood of causality. Related AEs will be reported to IRB. Nonrelated AEs will be tracked by the study team.

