## 8.3.2 EC/IRB Notification by Investigator

Reports of all serious adverse events (including follow-up information) must be submitted to the EC/IRB within 10 working days. Copies of each report and documentation of EC/IRB notification and receipt will be kept in the Clinical Investigator's binder.

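### Adverse event recording starts at the first dose, so the pre-dose FiO2 weaning maneuver has no scheduled AE entry; the promised venous blood gas is also unscheduled (minor)

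*Combined protocol and SAP*

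**What the plan says.** **AE window.** Section 8.1 (Adverse Event Reporting Period) first gives the usual window, "normally defined as the period from the initiation of any study procedures to the end of the study treatment follow-up". It then sets a different start for this trial: "For this study, subjects will be followed for AEs from the time of voxelotor administration until 2 days after the last administration of voxelotor". No reason is given. Section 8.2 repeats the start: "Subjects in this study will be followed for AEs from the time of voxelotor administration until 2 days after the administration of voxelotor". The AE row of Table 2 is marked from D1 to D7 and is blank on D-2 and D-1. In Section 6, an AE entry appears in 6.3 to 6.7 but not in 6.1 (screening) or 6.2 (the day before dosing).

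**Maneuver.** Section 3.1 takes the physiological data from standard care, with one exception: the S/F ratio, "which will be obtained at the same intervals but by the qualified and delegated study staff or medical team". It is measured by lowering FiO2 until SpO2 is about 88% and then restoring the prescribed oxygen. Table 2 marks the S/F ratio on all nine days, D-2 to D7. The pre-dose values are needed for the primary analysis (Section 7.2): "The baseline value will be defined as the median S/F ratio measurement during the 48-hour period before initiation of voxelotor treatment".

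**Broader wording.** Section 8.1 defines an AE as "any symptom, sign, illness or experience that develops or worsens in severity during the course of the study". Section 8.2 adds: "All adverse events occurring during the study period must be recorded". Section 8.3.2 says: "Reports of all serious adverse events (including follow-up information) must be submitted to the EC/IRB within 10 working days".

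**Venous blood gas.** Sections 1.5 and 4.4.1 promise venous gases (for metabolic acidosis) and renal function as checks that enough oxygen still reaches the tissues. The blood sampling paragraph of Section 3.1, Table 2 and Sections 6.1 to 6.7 list no venous gas.

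**The concern.** The maneuver deliberately brings oxygen-dependent patients down to an SpO2 of about 88%, and it is done for the study. Patients undergo it before they receive any drug, yet the AE window opens only with the drug. Someone following Table 2 and Section 6 would have no prompt to enter a non-serious event caused by the maneuver on those days. For a consented patient who has the maneuver and is never dosed, the window never opens.

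The pre-dose days matter more than their number suggests. In a single-arm trial they are the only maneuver days on which an event cannot be a drug effect. They are therefore the natural reference for judging whether later events on maneuver days come from the procedure or from voxelotor.

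The venous gas is a smaller matter: a safety measurement is promised twice but has no scheduled day.

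**Working it through.** The plan gives no event rate for the maneuver, so no number of missed events can be estimated. What can be checked is coverage by day.

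**1. Maneuver days against AE days (Table 2)**
- S/F ratio: D-2, D-1 and D1 to D7 = 9 days.
- AEs: D1 to D7 = 7 days.
- Maneuver days outside the AE window: 9 − 7 = 2 (D-2 and D-1); 2/9 = 22.2%.
- For 20 patients with complete follow-up: 2 × 20 = 40 of 9 × 20 = 180 patient-days.

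**2. The same count under Section 3.1**
- Section 3.1 gives the first dose the day after consent, whereas Table 2 and Section 6.1 place consent on D-2. The maneuver is not standard care, so it cannot precede consent. Under the Section 3.1 timing only D-1 is a pre-dose maneuver day.
- Uncovered: 1/8 = 12.5%, or 20 of 8 × 20 = 160 patient-days.

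**3. Section 6 entries**
- Subsections with an AE entry: 6.3, 6.4, 6.5, 6.6 and 6.7 = 5 of 7.
- Pre-dose subsections (6.1, 6.2) with one: 0 of 2.

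**4. Does the broader wording close the gap?**
- For serious events, partly. The AE definition covers the course of the study, and the IRB is to receive all SAEs.
- For non-serious events, not reliably. Section 8.1 introduces the reporting period and then starts it at dosing, so the study period in Section 8.2 can be read as starting there too. The schedule supports that reading.

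**5. Off-loading markers (Table 2)**
- Venous gas: 0 of 9 days.
- Renal chemistry: CMP on D-1 and D7, BMP on D1 to D6 = 8 days.
- Erythropoietin: D-1, D2 and D6 = 3 days.
- Arterial values are listed under the ALI cohort. Section 3.1 limits arterial gas samples to patients with an arterial line, and inclusion criterion 1 admits patients for whom no arterial gas can be obtained.

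**6. Blood volume**
- Stated in Section 3.1: 109 mL.
- Listed draws: erythropoietin 3 × 5 = 15; PK 8 × 2 = 16; P50 8 × 3 = 24; BMP 6 × 4.5 = 27; CMP 2 × 4.5 = 9; CBC 8 × 3 = 24; pregnancy test 2. Sum = 117 mL (115 mL without the pregnancy test).
- Difference: 117 − 109 = 8 mL (8/109 = 7.3%). The stated 109 mL is reproduced if PK, P50 and CBC are drawn on 7 days instead of 8: 117 − (2 + 3 + 3) = 109.
- Neither total includes a venous gas.

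**The case against.** **The window is a visible choice.** Section 8.1 states the usual window and departs from it, in a pilot with no primary safety endpoint. That is fair, but no reason is given, and the choice leaves out a procedure the study itself adds.

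**Other text softens the gap.** Section 8.2 tells the investigator to ask about AEs at every contact, and the Section 8.1 definition of an unanticipated problem covers risks of study procedures. A reader might infer that serious pre-dose events would go unreported. The documents do not support that; such events have a reporting route through the general wording. What stands is that the route is not tied to the pre-dose days, and that non-serious events have no scheduled entry.

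**The maneuver may be low risk.** FiO2 is lowered slowly and restored afterwards, and inclusion criterion 1 accepts patients managed to SaO2 above 85%. SpO2, FiO2, heart rate and Borg score are recorded on the pre-dose days. A reader might infer that the maneuver is harmful; the plan gives no data either way.

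**A wider window has a side effect.** Under Section 8.4, an SAE in any of the last 15 participants pauses enrollment, and an unexpected rate of expected SAEs halts it. Recording SAEs before dosing could let events of the underlying illness trigger these rules. This objection stands in full and narrows the fix.

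**The venous gas may still be done.** Table 2 also omits the ECG and urinalysis promised in Section 3.4, so absence from the table is weak evidence that a test will be skipped. A reader might infer that off-loading goes unmonitored, or that withdrawal depends on the missing gas. Neither holds. Renal chemistry and erythropoietin are scheduled, any patient with an arterial line may have arterial gases, and the Section 4.4.1 bullet is a monitoring statement with no threshold. What stands is that a promised test has no scheduled day.

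**Conclusion.** The AE point holds and should be fixed. As written, 1 or 2 pre-dose maneuver days per patient (12.5% or 22.2% of maneuver days) fall outside scheduled AE recording; the other seven are covered. The range reflects the plan's two consent timings, and the patient-day counts assume 20 patients with complete follow-up. The consequence is that procedure harm before dosing is not captured systematically. Neither a number of missed events nor a finding that the maneuver is unsafe follows from this.

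The venous gas omission and the blood volume mismatch are minor points of consistency. Part of the off-loading risk is already covered, and no defined withdrawal decision rests on the gas.

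A reader might also infer that the efficacy result is compromised. It is not: the S/F measurements, including the pre-dose baseline, are scheduled and unaffected by the AE window.

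**What to change.** **AE window (Sections 8.1, 8.2, 6.1, 6.2 and Table 2).** From the first study procedure after consent, record all SAEs and any AE that occurs during or is related to a study procedure. Include consented patients who are never dosed. Tabulate these events separately from treatment-emergent events.

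**Enrollment rules (Section 8.4, repeated in 4.4.1).** State that pre-dose events unrelated to a study procedure do not count toward the pause and halt rules.

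The cost is one or two more days of AE recording in inpatients who are already being measured on those days.

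**Venous gas (minor).** Add it, with pH, to Table 2 and Section 6 for both cohorts on D-1 (baseline) and D1 to D5, and restate the blood volume to match the listed draws. At an assumed 1 to 2 mL per draw, six draws add 6 to 12 mL, giving 117 + 6 = 123 to 117 + 12 = 129 mL.

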#### **Preexisting Condition**

A preexisting condition is one that is present at the start of the study. A preexisting condition should be recorded as an adverse event if the frequency, intensity, or the character of the condition worsens during the study period.

#### General Physical Examination Findings

At screening, any clinically significant abnormality should be recorded as a preexisting condition. At the end of the study, any new clinically significant findings/abnormalities that meet the definition of an adverse event must also be recorded and documented as an adverse event.

#### Post-study Adverse Event

All unresolved adverse events should be followed by the investigator until the events are resolved, the subject is lost to follow-up, or the adverse event is otherwise explained. At the last scheduled visit, the investigator should instruct each subject to report any subsequent event(s) that the subject, or the subject's personal physician, believes might reasonably be related to participation in this study. The investigator should notify the study sponsor of any death or adverse event occurring at any time after a subject has discontinued or terminated study

participation that may reasonably be related to this study. The sponsor should also be notified if the investigator should become aware of the development of cancer or of a congenital anomaly in a subsequently conceived offspring of a subject that has participated in this study.

#### Abnormal Laboratory Values

A clinical laboratory abnormality should be documented as an adverse event if any one of the following conditions is met:

- The laboratory abnormality is not otherwise refuted by a repeat test to confirm the abnormality
- The abnormality suggests a disease and/or organ toxicity
- The abnormality is of a degree that requires active management; e.g. change of dose, discontinuation of the drug, more frequent follow-up assessments, further diagnostic investigation, etc.

#### Hospitalization, Prolonged Hospitalization or Surgery

Any adverse event that results in hospitalization or prolonged hospitalization should be documented and reported as a serious adverse event unless specifically instructed otherwise in this protocol. Any condition responsible for surgery should be documented as an adverse event if the condition meets the criteria for and adverse event.

Neither the condition, hospitalization, prolonged hospitalization, nor surgery are reported as an adverse event in the following circumstances:

- Hospitalization or prolonged hospitalization for diagnostic or elective surgical procedures for a preexisting condition. Surgery should *not* be reported as an outcome of an adverse event if the purpose of the surgery was elective or diagnostic and the outcome was uneventful.
- Hospitalization or prolonged hospitalization required to allow efficacy measurement for the study.
- Hospitalization or prolonged hospitalization for therapy of the target disease of the study, unless it is a worsening or increase in frequency of hospital admissions as judged by the clinical investigator.

## 8.2 Recording of Adverse Events

At each contact with the subject, the investigator must seek information on adverse events by specific questioning and, as appropriate, by examination. Information on all adverse events should be recorded immediately in the source document of the case report form (CRF). All clearly related signs, symptoms, and abnormal diagnostic procedures results should be recorded in the source document, though should be grouped under one diagnosis.

All adverse events occurring during the study period must be recorded. The clinical course of each event should be followed until resolution, stabilization, or until it has been determined that the study treatment or participation is not the cause. Serious adverse events that are still ongoing at the end of the study period must be followed up to determine the final outcome. Any serious adverse event that occurs after the study period and is considered to be possibly related to the study treatment or study participation should be recorded and reported immediately.

Requirements for reporting of an AE to various entities (IRB, FDA, and Sponsor) differ according to whether or not the AE represents an unanticipated problem. This study will follow 21 CFR 312.32 IND Safety Reporting guidelines and DUHS prompt reporting to the IRB policy for events that occur with this study.

Subjects in this study will be followed for AEs from the time of voxelotor administration until 2 days after the administration of voxelotor as defined by study wash out period. The PI will be responsible for ensuring participants' safety.

[name] will be the physician responsible for reviewing and evaluating all adverse events. [name] will evaluate the safety of voxelotor treatment in all subjects by following adverse events and assigning likelihood of causality. Related AEs will be reported to IRB. Nonrelated AEs will be tracked by the study team.

# 8.3 Reporting of Serious Adverse Events

## 8.3.1 Study Sponsor Notification by Investigator

A serious adverse event must be reported to GBT within 24 hours of the event. A Serious Adverse Event (SAE) form must be completed by the investigator and faxed to the study sponsor within 24 hours. The investigator will keep a copy of this SAE form on file at the study site.

Report serious adverse events by email or facsimile to: [contact] or [name]

At the time of the initial report, the following information should be provided:

- Study identifier
- Study Center
- Subject number
- A description of the event
- Date of onset
- Current status

- Whether study treatment was discontinued
- The reason why the event is classified as serious
- Investigator assessment of the association between the event and study treatment

Within the following 48 hours, the investigator must provide further information on the serious adverse event in the form of a written narrative. This should include a copy of the completed Serious Adverse Event form, and any other diagnostic information that will assist the understanding of the event. Significant new information on ongoing serious adverse events should be provided promptly to the study sponsor

